### **8.1.3 Secondary analyses of the primary efficacy variables**

Not applicable.

### **8.1.4 Supportive and sensitivity analyses of the primary efficacy variables**

The primary analyses (ANCOVA and corresponding summary statistics) will be repeated for the PPS on observed cases.

In case of misallocation to treatment groups, the primary analyses will be repeated for the FAS as randomized.

## **8.2 Analysis of other efficacy variables**

### **8.2.1 Kinesia-360 motor scores**

Kinesia-360-based efficacy data will be presented descriptively for the Experimental Group. Due to repeated measurements (during titration weekly and during maintenance), comparisons will be

performed by time point and also by dose, if applicable (dependent on number of subjects in respective dose groups). Optional time points might also be subject to analysis (dependent on number of subjects at respective time points or windows for time points).

Change from Baseline to Week 2, Week 3, Week 4, Week 7/8, and Week 11 in the motor scores derived from the Kinesia-360 wearable technology by Neupro dose level (mg/24h) for the Experimental Group will be summarized for following scores:

- average daily tremor score
- average daily slowness score
- average daily dyskinesia score
- percent wear-time tremor detected
- percent wear-time dyskinesia detected
- percent wear-time user not moving
- percent wear-time user was walking score
- percent wear-time user active but not walking
- number of steps per hour while wearing device

The average daily scores of tremor, slowness and dyskinesia will be derived from the 2-minutes interval data. Only those 2-minutes interval data records, when the device was not paused, will be considered. For each day, starting at 0:00 until 23:58, the available non-paused 2-minutes interval scores of tremor (and similarly for slowness and dyskinesia) will be selected and the arithmetic mean of these will be calculated which results in the average daily scores.

The percent wear-times and number of steps per hour will be derived from the daily Kinesia-360 data. Multiple records per day will be averaged and weighted by wear-time.

These daily scores will be used to derive the scores per visit week. The daily scores will be averaged from 2 consecutive days of wearing in the respective assessment week. Assessments on study day 8 to 14 are eligible for Week 2 scores, assessments on study day 15 to 21 are eligible for Week 3 scores, assessments on study day 22 to 28 are eligible for Week 4 scores, assessments on study day 43 to 56 are eligible for Week 7/8 scores, and assessments on study day 71 to 77 are eligible for Week 11 assessments. The Week 7/8 is an artificially added Week, which considers the data collected on voluntary basis during that time interval, and therefore might have sparse data. If more than 2 consecutive assessments are available for Week 7/8, the latest 2 consecutive values will be considered. The same applies for the assessments in Week 2, Week 3, Week 4, and Week 11: If more than 2 consecutive assessments are available per week, the latest 2 consecutive values will be considered.

In addition, the maximum relative day of Kinesia-360 usage will be listed, and the number of days the subject used the Kinesia-360 device will be calculated by subject and summarized.

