4.1.2 Other efficacy variables

- Change from Baseline to Visit 2 in the motor scores derived from the Kinesia-360 wearable technology by time (weekly/monthly) and by Neupro dose level (mg/24h) for the Experimental Group in:
 - average daily tremor score
 - average daily slowness score
 - average daily dyskinesia score
 - percent wear-time tremor detected
 - percent wear-time dyskinesia detected
 - percent wear-time user not moving
 - percent wear-time user was walking score
 - percent wear-time user active but not walking

- number of steps per hour while wearing device
- Change from Baseline to Visit 2 (Week 12) in the 39-Item Parkinson's Disease Questionnaire (PDQ-39) scores.
- Change from Baseline to Visit 2 (Week 12) in subject engagement questionnaire scores.

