5 STUDY DESIGN

5.1 Study description

PD0049 is a multicenter, open-label, two-arm, 12-week study in subjects with Parkinson's disease. On Day 1, eligible subjects will be randomized to either the Control Group or the Experimental Group in a 1:1 fashion. In both groups, subjects will use the Kinesia-ONE wearable device in-clinic at Visit 1 and Visit 2 for recording of specific motor symptoms, and subjects randomized to the Experimental Group will also use the Kinesia-360 wearable device at home while awake for continuous measurement of motor symptoms. The Investigator will use these symptom data to provide feedback to subjects on their motor symptoms and to supplement standard of care to titrate the optimal dose of Neupro for any given subject. In the Control Group, subjects will not use any wearable device at home, and the Investigator will use only standard of care to titrate the optimal Neupro dose.

Subjects in the Control Group and the Experimental Group will start treatment with Neupro 2mg/24h or 4mg/24h (at the Investigator's discretion and according to the disease stage of the subject) preferably on Day 1 (but no later than Day 4) or Day 4, respectively. Evaluations conclude 12 weeks after the start of treatment with Neupro (ie, at Visit 2).

The decision to prescribe Neupro must be made by the Investigator independent of his/her decision to include the subject in the study. The subject's treatment/Neupro intake must be within the terms of the marketing authorization; Neupro will not be supplied by UCB.

A schedule of study assessments is presented in [Table 5-1](#); for a detailed rationale of the study design see [Section 5.3](#).

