5.2 Schedule of study assessments

A schedule of assessments planned for both the Control Group and the Experimental group is presented in [Table 5-1](#).

This document cannot be used to support any marketing authorization application and any extensions or variations thereof.

REDACTED COPY

Table 5–1: Schedule of study assessments

Assessments	In Clinic		At Home					In Clinic
	SCREENING	BASELINE						EOS/EW
	Visit 1						Visit 2	
	Day 1	Day 2-3	Day 4	Week 2	Week 3	Week 4	Week 11	Week 12 (±3 days)
Written informed consent	X							
Demographic data (incl. height and weight)	X							X ^a
Kinesia-ONE subject assessments (measured in triplicate)	X ^b							X
UPDRS	X							X
Patient engagement questionnaire	X							X
PDQ-39	X							X
Verification of inclusion/exclusion criteria	X							
Randomization	X							
C Group: Start treatment with Neupro 2mg or 4mg preferably on Day 1 but no later than Day 4 (dose adjustments during study are performed per standard of care)		X						X
C Group: Record Neupro dose		X						X
E Group: Kinesia-360 device training and distribution of equipment	X							
E Group: Subject wears Kinesia-360 wrist and ankle devices on Days 2 and 3 at home for baseline			X					
E Group: Start treatment with Neupro 2mg or 4mg on				X				

Day 4								
E Group: Record Neupro dose ^c			X					X
E Group: Reminder phone calls from site to subject at beginning of Weeks 2, 3, 4 and 11 (remind subject to charge devices and wear devices on at least 2 consecutive days during Weeks 2, 3, 4 and 11)				X ^d	X ^d	X ^d	X ^d	
E Group: Subject wears Kinesia-360 wrist and ankle devices on at least 2 consecutive days at home				X	X	X	X	
E Group: Subject and Investigator access Kinesia-360 device reports (subjects via device app, Investigators via GLNT web portal)					X			X
E Group: Investigator combines standard of care with Kinesia-360 motor symptom reports to adjust Neupro dose and is encouraged to contact the subject by phone to discuss motor symptom reports and potential Neupro dose adjustments anytime between V1 and V2 based on clinical judgment					X			
E Group: Subject returns Kinesia-360 device equipment to site								X
Record adverse events	X							X
Record concomitant medications	X							X

APP=application; C Group=Control Group; E Group=Experimental Group; EOS=End of Study; EW=Early Withdrawal; GLNT=Great Lakes Neuro Technologies, Inc.; PDQ-39=39-Item Parkinson's disease questionnaire; UPDRS=Unified Parkinson's Disease Rating Scale; V=visit

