- A reminder phone call from the site to the subject each week during Weeks 2, 3, and 4 to ensure the subject will perform the protocol-requested Kinesia-360 assessments on 2 consecutive days per week. In addition, the subject should be reminded to charge the device and phone batteries the night prior to assessments.

8.4 Week 5 up to Week 12

Control Group, home:

- Treatment of subjects as per standard of care.
- Phone contact initiated by subject or Investigator as needed. Documentation of any contact or dosage adjustment.

Experimental Group, home:

- A reminder phone call from the site to the subject during the week prior to Visit 2 to ensure the subject will perform the protocol-requested Kinesia-360 assessments on 2 consecutive days. In addition, the subject should be reminded to charge the device and phone batteries the night prior to assessments.
- Optional: Subject may use Kinesia-360 as desired between Week 5 and Visit 2 (Week 12).
- Subject receives Kinesia-360 motor symptom reports on device following each day of measurements.

- Investigator receives Kinesia-360 motor symptom reports via web portal and by email following each day of measurements.
- Treatment of patients as per standard of care and dispatch of any Kinesia-360 motor symptom report.
- Phone contact initiated by subject or Investigator as needed and dispatch of Kinesia-360 motor symptom reports. Documentation of any contact or dosage adjustment.

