8.5 Visit 2 (End of Study Visit) (Week 12 ±3 days)

Visit 2 represents the 3 month (from first Neupro dose) Follow-Up Visit.

Control Group and Experimental Group, in clinic:

- Control Group and Experimental Group: Subject wears Kinesia-ONE sensor in the clinic on the same side assessed at Visit 1 to measure specific motor tasks in triplicate.
- Investigator performs UPDRS assessment
- Patient Engagement Questionnaire
- Record Neupro dose
- Complete questionnaire (PDQ-39)
- Recording of AEs and concomitant medications

Experimental Group, in clinic:

- Return Kinesia-360 equipment to site

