## **3.2 General study level definitions**

### **3.2.1 Analysis time points**

#### **3.2.1.1 Relative Day**

The relative day of a visit or an event with respect to the first administration of study medication (i.e. first patch application of Neupro) will be presented in subject data listings. Relative days will be calculated as follows:

- If the start (stop) date occurred prior to the first application of study medication, the relative day is calculated as start (stop) date minus date of first patch application. That means that in subject data listings, relative days based on this situation will be preceded by a '-'.
- If the start (stop) date occurred on or after the first application of study medication but prior to the last patch application, the relative day is calculated as start (stop) date minus date of first patch application + 1.
- If the start (stop) date occurred after the date of last patch application, the relative day is calculated as start (stop) date minus date of last patch application + 1. In subject data listings, relative days based on this situation will be preceded by a '+'.

Relative days will not be presented for partial or missing dates.

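### When Visit 2 is timed from first dose, a Kinesia-360 recording made in the week before Visit 2, as Protocol 8.4 implies, falls after the SAP's last window (Day 71-77) and enters no time point

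*SAP*

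**What the plan says.** **Analysis windows.** SAP 8.2.1 assigns Kinesia-360 recordings to Weeks 2, 3, 4, 7/8 and 11 by study day. The first rule reads "Assessments on study day 8 to 14 are eligible for Week 2 scores" and the last reads "assessments on study day 71 to 77 are eligible for Week 11 assessments". Nothing after Day 77 has a window. Each weekly score averages two consecutive days, the latest two if there are more.

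**Variable.** Protocol 4.1.2 and SAP 2.2.1.2 both name it as "Change from Baseline to Visit 2 in the motor scores derived from the Kinesia-360 wearable technology".

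**When the last recording is requested.** The protocol gives two answers. Table 5-1 schedules "Reminder phone calls from site to subject at beginning of Weeks 2, 3, 4 and 11", with wear in the same weeks. Section 8.4 (Week 5 up to Week 12) instead asks for "A reminder phone call from the site to the subject during the week prior to Visit 2", to make sure the two requested days of wear take place.

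**When Visit 2 occurs.** Protocol 5.1 states "Evaluations conclude 12 weeks after the start of treatment with Neupro (ie, at Visit 2". Section 8.5 also counts from first dose, under the title "Visit 2 (End of Study Visit) (Week 12 ±3 days". The protocol summary starts Neupro on Day 4 in the Experimental Group, but caps participation at 12 weeks.

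**Day count.** SAP 8.2.1 does not define *study day*. The only count the SAP defines is in 3.2.1.1: "The relative day of a visit or an event with respect to the first administration of study medication". It is introduced there for data listings.

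**The concern.** A reminder call is useful only for wear that has not yet happened, and the equipment is returned at Visit 2. A call made in the week before Visit 2 therefore leads to wear in that same week. If Visit 2 is counted from first dose, that week lies after Day 77 and the recording closest to Visit 2 reaches no summary table. A subject recorded on the Table 5-1 schedule would contribute to the last time point, while one recorded on the 8.4 schedule would not. In a group of about 20, a few such cases would visibly thin the last column.

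Separately, the variable is named as change to Visit 2 but is analysed only to Week 11, and SAP 3.9 does not list this as a change from the protocol.

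**Working it through.** **Step 1. Reproduce the SAP windows.** With protocol Day 1 (Visit 1) as day 1, week w runs from day 7(w − 1) + 1 to day 7w.

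- Week 2: 8-14. Week 3: 15-21. Week 4: 22-28.
- Weeks 7 and 8 together: 43-56.
- Week 11: 71-77.

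All five match SAP 8.2.1 exactly, so the windows are built on a count from Visit 1.

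**Step 2. Place Visit 2.** First dose on Day 4 plus 12 × 7 = 84 days gives Day 88. The 3-day tolerance gives Day 85 to 91.

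**Step 3. Compare the week before Visit 2 with Day 71-77.** For a visit on Day V, the preceding week is Day V − 7 to V − 1. It holds 6 pairs of consecutive days. An overlap of n days with the window (n ≥ 1) leaves n − 1 usable pairs.

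| Visit 2 on Day | Preceding week | Days inside 71-77 | Usable pairs of 6 |
|---|---|---|---|
| 78 (first day of Week 12) | 71-77 | 7 | 6 |
| 81 | 74-80 | 4 | 3 |
| 82 | 75-81 | 3 | 2 |
| 83 | 76-82 | 2 | 1 |
| 84 (last day of Week 12) | 77-83 | 1 | 0 |
| 85 (earliest, first-dose anchor) | 78-84 | 0 | 0 |
| 88 (nominal, first-dose anchor) | 81-87 | 0 | 0 |
| 91 (latest, first-dose anchor) | 84-90 | 0 | 0 |

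Days 86, 87, 89 and 90 also give 0. On the first-dose anchor the exclusion is complete. For a visit inside Week 12 the result depends on the day: all 6 pairs qualify on Day 78, none on Day 84.

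**Step 4. How far a captured value lies from Visit 2.** With Visit 2 on Day 88, a recording in Day 71-77 precedes it by 88 − 77 = 11 to 88 − 71 = 17 days.

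**Step 5. Would another day count change the result?** If study day were read as the SAP's Relative Day, with first patch on Day 4, protocol day = relative day + 3 and the last window becomes protocol Day 74-80. The preceding week then overlaps it by 3 days (2 pairs) for a visit on Day 85, by 2 days (1 pair) on Day 86, by 1 day (no pair) on Day 87, and by 0 on Days 88 to 91. The nominal visit is still missed.

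**The case against.** The best defence is that the window is right and the protocol text is loose. Day 71-77 is Week 11 of Table 5-1, the last column before Visit 2, and 8.4 can be read as referring to that same week. Days 85 to 91 are Week 13 on the Day 1 count, which sits badly with a visit labelled Week 12 and with participation of up to 12 weeks. This stands in part. A reader might infer that the SAP discards the requested recording outright, and the documents do not support that: a recording on the Table 5-1 schedule is kept, and a visit early in Week 12 fits the window. But Protocol 5.1 and 8.5 both count Visit 2 from first dose, and on that count the loss is complete.

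A reader might also infer that the SAP's own day count moves every weekly window by three days. That is not shown. The SAP never equates study day with Relative Day, introduces Relative Day for listings, uses the two terms separately within 8.2.1, and sets windows that match the protocol weeks from Day 1 with no shift. What is missing is a definition. Nor would a shift add to the first problem, since it would move the last window later and slightly reduce the exclusion.

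It can also be said that the data are not lost, because everything is listed by subject and SAP 8.2.1 allows optional time points to be analysed. That is true, but the allowance is discretionary and sets no window after Day 77. Finally, the documents do not show which schedule sites followed, so the number of subjects affected is unknown.

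**Conclusion.** The point holds as a conditional gap. If Visit 2 is 12 weeks after a Day 4 first dose, and the last wear takes place in the week before it, none of the 6 possible two-day pairs falls in Day 71-77 for any visit from Day 85 to 91, and no other window takes the recording. The source is a conflict within the protocol, between 8.4 and Table 5-1 and over where Week 12 is counted from. The SAP follows the table and does not provide for the other reading, while keeping a variable name that refers to Visit 2.

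The impact is minor. Kinesia-360 scores are among the *other* efficacy variables, summarised descriptively in the Experimental Group only, so no between-group comparison or test is affected. The undefined study day is missing detail, not an error in the windows.

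**What to change.** 1. In SAP 8.2.1, keep Day 71-77 as the first choice for the last time point. If it holds no two consecutive days, use the latest two consecutive days from Day 78 to the day before Visit 2. Alternatively, summarise Day 78 to Visit 2 as a separate window.
2. Label the time point for what it contains. If Day 71-77 is kept alone, name the variable as change to Week 11 and record this in SAP 3.9.
3. Reconcile Protocol 8.4 with Table 5-1, so that the last requested recording has one stated time.
4. State in SAP 8.2.1 that study day 1 is Visit 1. This is a clarification and moves no window.

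A single window from Day 71 to the day before Visit 2, combined with the existing latest-two rule, would be a worse choice. Protocol 8.4 allows voluntary wear up to Visit 2, so that rule would replace scheduled Week 11 recordings with later optional ones.

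The cost is a few sentences. The timing of the last point would vary more between subjects, from Day 71 to as late as Day 90 for a Day 91 visit; a separate window avoids mixing the two periods. Because SAP Amendment 1 was written after the Data Evaluation Meeting, any further change should be dated and identified as made after that meeting.

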## **8.2.2 Parkinson's Disease Questionnaire (PDQ-39)**

The Parkinson's Disease Questionnaire (PDQ-39; Jenkinson, 1997) is a simple questionnaire that assesses health related quality of life in individuals with PD. The answer categories are coded as follows: 0=never, 1=occasionally, 2=sometimes, 3=often, 4=always or cannot do at all. It

provides scores in 8 scales: mobility (questions 1-10), activities of daily living (questions 11-16), emotions (questions 17-22), stigma (questions 23-26), social support (questions 27-29), cognition (questions 30-33), communication (questions 34-36), and bodily discomfort (questions 37-39). It is designed for self-completion by subjects and should take only a few minutes for the subject to complete.

For each of the 8 domains a score will be calculated: The coded answer categories of the corresponding domain questions will be added. This domain raw value will be multiplied with 100 and divided by the maximum domain raw value (e.g.  $4*10=40$  for the 10 questions of mobility domain). This transformation gives domain scores between 0 and 100.

Domain scores will only be calculated if at least 50% of items on the scale have been answered. If this is the case, the missing items, if any, will be replaced with the overall mean of the item, and the corresponding domain score will be calculated based on the replaced questions.

The social support domain consists of questions 27, 28, and 29. If respondents indicate that they do not have a spouse or partner on question 28 then social support will be calculated as follows: social support = (sum of questions 27 + 29) / (4 \* 2) \* 100.

Individual questions will be summarized categorically, and the domain scores will be tabulated using continuous summary statistics by visit.

A sum score, calculated by adding together the 8 domain scores and dividing the sum by 8, will also be presented using continuous summary statistics by visit (including change from baseline values).

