### **8.2.3 Patient Activation Measure (PAM-13)**

The Patient Activation Measure (PAM-13) quantifies the extent to which people are informed about and involved in their health care. The answer categories are coded as follows: 1=disagree strongly, 2=disagree, 3=agree, 4=agree strongly.

A sum score will be calculated by adding together the coded answer categories of the 13 items, and then transforming to a scale from 0 to 100 using the formula  $100*(\text{sum of items} - 13)/(52 - 13)$ .

The sum score will only be calculated if at least nine questions have been answered. If this is the case, the missing items, if any, will be replaced with the overall mean of the item, and the sum score will be calculated based on the replaced items.

The individual questions will be summarized categorically, and the sum score will be presents using continuous summary statistics by visit (including change from baseline values).

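### Missing PDQ-39 and PAM-13 items are replaced by an across-subject item mean; if pooled over groups, this shrinks the group difference by about the share of items missing

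*SAP*

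**What the plan says.** **PDQ-39 (SAP 8.2.2).** The completeness threshold is: "Domain scores will only be calculated if at least 50% of items on the scale have been answered". Above it, "the missing items, if any, will be replaced with the overall mean of the item". The domain is then scaled to 0-100 by its maximum raw value.

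**PAM-13 (SAP 8.2.3).** "The sum score will only be calculated if at least nine questions have been answered". Missing items are then "replaced with the overall mean of the item, and the sum score will be calculated based on the replaced items".

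Neither section says over which group, visit or analysis set the item mean is taken.

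**The exception.** In the social support domain, a subject who reports having no partner at question 28 is scored from the two remaining answers: "social support = (sum of questions 27 + 29) / (4 \* 2) \* 100".

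**Related rules.**
- Protocol 12.6 says that missing data will in general not be imputed.
- SAP 8.1.1.1 and 8.2.4 set the UPDRS Part III and Part II sum scores to missing if any item is missing.
- SAP 4.2 deals with withdrawal visits, adverse event attributes and partial dates, but not with questionnaire items.
- SAP 3.9 lists only the added Kinesia-ONE scores as a change from the protocol.

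**The concern.** The mean of an item is an average over people. A subject who answers most of a domain at the severe end, and skips one question, receives the typical subject's answer to that question. Scores at either end are pulled toward the middle. If the mean combines both groups, the same constant is inserted in each, so part of any true group difference is removed.

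At stake are the quality-of-life and engagement objectives (Protocol 3.2), which rest on these two questionnaires, with about 20 subjects per group. The rule is also under-specified: two programmers could reasonably choose different groups, visits or analysis sets for the mean and obtain different scores.

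**Working it through.** **Scale checks.** The mobility maximum is 4 × 10 = 40, as the SAP states. The PAM-13 transformation gives 100 × (13 − 13)/39 = 0 and 100 × (52 − 13)/39 = 100, so it spans the intended range. The plan gives no item-missing rate, item mean or expected effect, so those below are assumptions.

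**Expected values for one item.** Let a share m of its values be missing at random, alike in both groups, with group means μE and μC, and let c be the inserted constant.
- Mean pooled over groups: difference = [(1 − m)μE + mc] − [(1 − m)μC + mc] = (1 − m)(μE − μC), whatever c is. Item difficulty plays no part.
- Mean taken within group: the inserted value has expectation μE or μC, so the expected difference is kept.
- Change from Baseline in group g, with mean true change Δg, inserted constants c1 and c2 at the two visits, and m the same at both: (1 − m)Δg + m(c2 − c1). If the mean is pooled over visits, c1 = c2 and the change becomes (1 − m)Δg. If it is taken per visit, each group's change is pulled toward the common change, not toward zero. The group difference in change shrinks by (1 − m) either way.

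**Simulation.** Assumed inputs: 20 per group; 10 equally difficult items scored 0-4; subject means centred at 1.8 and 2.3 with SD 0.8; item noise SD 0.7; items missing at random; the 50% threshold applied; 1,500 runs. Entries are group difference / within-group SD, in points on the 0-100 scale.

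| Items missing | Complete data | Pooled item mean | Own-scale mean |
|---|---|---|---|
| 1% | 11.97 / 19.63 | 11.85 / 19.45 | 11.97 / 19.64 |
| 5% | 11.90 / 19.68 | 11.31 / 18.78 | 11.92 / 19.73 |
| 10% | 11.83 / 19.62 | 10.63 / 17.78 | 11.85 / 19.73 |
| 20% | 11.75 / 19.61 | 9.36 / 15.96 | 11.75 / 19.85 |
| 30% | 11.77 / 19.64 | 8.30 / 14.40 | 11.76 / 20.03 |

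The ratio of pooled-mean to complete-data difference is 11.85/11.97 = 0.99, 11.31/11.90 = 0.95 and 10.63/11.83 = 0.90 at 1%, 5% and 10%, in line with 1 − m.

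Because the SD shrinks as well, the standardised difference hardly moves: at 10%, 10.63/17.78 = 0.598 against 11.83/19.62 = 0.603. The distortion is in the estimate and SD in points.

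A within-group item mean keeps the difference (11.81 against 11.82 at 10%) but still understates the SD (17.83 against 19.71). The standardised difference then becomes 11.81/17.83 = 0.662 against 11.82/19.71 = 0.600, which is too large.

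**One subject, assumed item means of 1.0 to 2.0.** Nine mobility items answered 4 and one missing: 100 × (36 + 1.0)/40 = 92.5 to 100 × (36 + 2.0)/40 = 95.0, against 100 with the own-scale mean. At the permitted limit of five missing: 100 × (20 + 5 × 1.0)/40 = 62.5 to 100 × (20 + 5 × 2.0)/40 = 75.0, against 100.

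**Question 28.** Let a and b be the answers to questions 27 and 29. Own-mean replacement gives 100 × [a + b + (a + b)/2]/12 = 100 × (a + b)/8, which is exactly the SAP's no-partner formula. So the SAP already uses own-scale scoring for a subject without a partner, and the item mean for one who leaves the same question blank.

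**The case against.** **The SAP does not say that the mean ignores visit or group.** This stands. The word *overall* favours pooling over groups, but nothing states pooling over visits. A reader might infer that change from Baseline is generally driven toward zero; the text does not support that, because with a per-visit mean the average change over the two groups is preserved.

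**Large individual figures are corner cases.** This also stands. A reader might take the gap between 62.5 and 100 as an error of 37.5 points. It is the distance between two replacement rules, for a subject at ceiling with the most missing items allowed, and it treats the unseen answers as 4. No document supports that.

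**The own-scale mean is not better in every case.** True. Take an illustrative stable subject answering 3, 3, 0 in a three-item domain at Baseline (6/12 = 50) who skips the third item at Visit 2. The own-scale mean gives 9/12 = 75, a spurious change of 25 points. An item mean of 0.3 gives 6.3/12 = 52.5. The group comparison is a different matter: when items are missing alike in both groups, item difficulty affects both equally and cancels from the difference.

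**Little depends on it.** Largely true. SAP 2.2.1.2 lists both questionnaires among the other efficacy variables. SAP 8.2.2 and 8.2.3 plan only summary statistics for them, although SAP 4.1 is worded broadly enough to bring in ANCOVA. SAP 4.5 makes every test exploratory. Individual questions are tabulated, and SAP 3.1 requires a row for missing values, so the extent of missing items will be visible.

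**Protocol 12.6 says only that imputation is avoided in general.** That leaves room for an exception, but an exception belongs in SAP 3.9, where it is absent.

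**Conclusion.** The point holds as a minor one. The SAP fills missing PDQ-39 and PAM-13 items from other people's answers. If the mean is pooled over both groups, the expected group difference in an item shrinks by about its share of missing values: 1-5% at 1-5% missing and 10% at 10%. The within-group SD is understated too. This assumes items missing at random and alike in both groups.

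Shrinkage of change within a group toward zero needs the further assumption of pooling over visits. The actual missing rate is unknown, and where no item is missing nothing changes. No primary variable is affected, and a reader should not infer that the study's main conclusions are at risk. The case for acting is that the change is cheap, removes an ambiguity and aligns the rule with the SAP's own handling of question 28.

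**What to change.** - In SAP 8.2.2, keep the 50% threshold and replace a missing item by the mean of the same subject's answered items in that domain at the same visit.
- In SAP 8.2.3, keep the nine-item threshold and do the same with the subject's answered PAM-13 items at that visit.
- In SAP 3.9, list this item imputation as a departure from Protocol 12.6.

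The cost is one phrase in each of two sections and one sentence in a third, with no new data and no subjects lost. The SAP should acknowledge the price: in short domains with very unequal items, one subject's score can be less accurate under the own-scale mean. Specifying a within-group item mean instead would not be a good repair, since it keeps the difference but leaves the SD too small.
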